9.10 Sexual Risk Behaviors

To assess the 744LA effect on sexual risk behavior by change from enrollment during the study period, the behavioral questionnaire (BQ) will be administered at the baseline (at

enrollment date) and at each injection visit week (Weeks 5, 17, 29 in Cohort 1 and 5, 9, 17, 25, 33 in Cohort 2) and tail visit weeks 41, 53, 65 and 77.

We will first assess whether or not there is any change in the sexual risk behavior at Week 5 from enrollment within each treatment arm and whether or not the change differs between the 744LA arm and the placebo arm. Then we will assess whether or not there is any change in the sexual risk behavior during the injection phase from the baseline (at Week 5) within each treatment arm and whether or not the change differs between the treatment arms over time using GEE model. The sexual risk behavior variables, such as the number of sexual partners, the number of total sexual acts, the episodes of unprotected anal and/or vaginal intercourse, the number of unprotected sexual acts with HIV seropositive partner(s) in the past 3 months, are as the outcomes and are assumed with a negative binomial distribution. The treatment and time are as covariates. Both analyses will be stratified by gender and adjusted for other demographic variables such as age and race/ethnicity. Robust standard errors will be used to account for within-person correlation. In the second analysis, time is treated as a continuous variable measured in 3 months; a linear and quadratic time and time interactions with the treatment are included in the model to test a linear or a quadratic trend in the self-reporting risk behavior in the past 3 months during the injection phase in each arm and to test the difference between the treatment arms. The data will be analyzed in aggregate.

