3.2 Secondary Objectives and Endpoints

Secondary Objectives

- Evaluate the safety and tolerability of GSK1265744 (daily oral 744 + 744LA) for 76 weeks of follow-up after final injection (each cohort will be analyzed separately)
- Evaluate the safety and tolerability of oral 744 from Week 0 to Week 5

- Evaluate the pharmacokinetics of 744LA administered as 800 mg IM every 12 weeks for 52 weeks of follow-up after final injection
- Evaluate differential pharmacokinetics of 744LA in participants by age, gender, race, ethnicity, weight, body mass index (BMI), and smoking status
- Evaluate the acceptability of 744LA injections
- Evaluate the effect of 744LA on sexual risk behavior by change from enrollment for repeat assessments to during the study period
- Evaluate HIV incidence and antiretroviral drug resistance, if any participants acquire HIV infection during the study
- Evaluate the safety, tolerability and pharmacokinetics of 744LA in the subset of women who use a hormone-based contraceptive

Secondary Endpoints

- Proportion of participants who discontinue either oral or injectable study product for reasons of toxicity, tolerability, or acceptability prior to completion of the full oral and injectable phases
- Proportion of participants experiencing Grade 2 or higher clinical AEs and laboratory abnormalities during 52 weeks following final injection (safety) and any AE that leads to discontinuation (tolerability) during the aggregate oral and injectable phases
- Proportion of participants experiencing Grade 2 or higher clinical AEs and laboratory abnormalities (safety) and any AE that leads to discontinuation (tolerability) in the oral phase and washout period
- Plasma drug levels of GSK1265744 at designated time points after each injection of 744LA (by cohort only)
- Plasma drug levels of GSK1265744 at designated time points after each injection of 744LA stratified by age, gender, race, ethnicity, weight, BMI, and smoking status
- Proportion of participants willing to use an injectable agent such as the study product for HIV prevention in the future
- Change from enrolment of self-reported sexual behaviour (number of sexual partners, episodes of unprotected anal and/or vaginal intercourse) during the study period using a standardized assessment tool (in aggregate only)
- Number of incident HIV infections through the study period, including number with treatment emergent resistance

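### With a 3-month recall, the Week 5 and Cohort 2 Week 9 sexual-behaviour contrasts are attenuated, and the Week 5 baseline moves oral-phase change into the injection phase

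*SAP*

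**What the plan says.** The secondary endpoint in SAP section 3.2 is "Change from enrolment of self-reported sexual behaviour".

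Section 9.10 schedules the behavioural questionnaire at enrolment, at each injection visit ("Weeks 5, 17, 29 in Cohort 1 and 5, 9, 17, 25, 33 in Cohort 2"), and at Weeks 41, 53, 65 and 77. The outcome list ends with "the number of unprotected sexual acts with HIV seropositive partner(s) in the past 3 months", and the trend model is said to concern "self-reporting risk behavior in the past 3 months during the injection phase in each arm". No other recall period is given.

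Two analyses follow:

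1. A test of "any change in the sexual risk behavior at Week 5 from enrollment within each treatment arm", and of whether that change differs between arms.
2. A negative binomial GEE of change "during the injection phase from the baseline (at Week 5) within each treatment arm". It has linear and quadratic time in 3-month units, time-by-treatment interactions and robust standard errors.

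The data are analysed with the cohorts pooled. The section gives no shorter recall for closely spaced visits, no offset for window length and no rule for overlapping windows.

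**The concern.** An answer covering the past 3 months describes only the time since the last questionnaire if the visits are about 3 months apart. Week 5 comes 5 weeks after enrolment, and Cohort 2 Week 9 comes 4 weeks after the first injection. Both answers therefore carry a large share of earlier behaviour.

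The objective is to find out whether taking the product changes risk behaviour. A formal Week 5 test showing no change would be partly built in by the shared window. A Week 5 baseline that blends pre-enrolment and oral-phase behaviour cannot separate oral-phase from injection-phase change, which is the purpose of the two-step analysis. Nor does it estimate the change from enrolment that section 3.2 names.

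**Working it through.** The SAP states no effect size or power for this analysis, so there is no figure of its own to reproduce. The check is the overlap of recall windows.

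**Inputs.** The visit weeks and the 3-month recall are from section 9.10. The first injection at Week 5 is from sections 2.3 and 7.1. Converting 3 months to R = 12 or 13 weeks is an assumption, and both are shown. Weeks 0 to 5 comprise 4 weeks of tablets and 1 week of washout.

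**Window composition.** An answer at week v covers v − R to v.

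| Visit | R | Window | Before enrolment | Weeks 0-5 | After first injection |
|---|---|---|---|---|---|
| Week 5 | 12 | −7 to 5 | 7/12 = 58% | 5/12 = 42% | 0% |
| Week 5 | 13 | −8 to 5 | 8/13 = 62% | 5/13 = 38% | 0% |
| Week 9 (Cohort 2) | 12 | −3 to 9 | 3/12 = 25% | 5/12 = 42% | 4/12 = 33% |
| Week 9 (Cohort 2) | 13 | −4 to 9 | 4/13 = 31% | 5/13 = 38% | 4/13 = 31% |
| Week 17 | 12 | 5 to 17 | 0% | 0% | 100% |
| Week 17 | 13 | 4 to 17 | 0% | 1/13 = 8% | 12/13 = 92% |

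All later windows lie wholly after the first injection.

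**Effect on the contrasts.** Expected rate ratios weight the true rate by time in the window, relative to a pre-enrolment rate of 1. The step sizes are illustrative assumptions. Paired results are for R = 12 / 13.

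- *Rate ratio 1.5 from enrolment, sustained.*
  - Week 5 against enrolment: 1 + 0.5 × 5/12 = 1.21, or 1 + 0.5 × 5/13 = 1.19. The truth is 1.50.
  - Week 17 onward against Week 5: 1.5/1.208 = 1.24, or 1.5/1.192 = 1.26. The truth is 1.00, because nothing changed at injection.
- *Rate ratio 1.5 from first injection.*
  - Cohort 2 Week 9 against Week 5: 1 + 0.5 × 4/12 = 1.17, or 1 + 0.5 × 4/13 = 1.15. The truth is 1.50.
  - Week 17: 1.50, or 1 + 0.5 × 12/13 = 1.46. Later visits: 1.50.
- *1.25 in the oral phase, then 1.5.*
  - Week 17 onward against Week 5: 1.35-1.37. The truth is 1.5/1.25 = 1.20.
- *1.5 in the oral phase only, then back to 1.0.*
  - Week 17 onward against Week 5: 0.83 for R = 12; 0.87 at Week 17 and 0.84 later for R = 13. The true fall is 1.0/1.5 = 0.67.

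The Week 5 and Week 9 contrasts are always diluted. The error in the later contrasts against Week 5 depends on what happened in the oral phase, and it can go either way.

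**Anchored at enrolment.** In the first pattern, Week 17 onward against enrolment gives 1.50 for either R. In the third it gives 1.50, or (1.25 × 1 + 1.5 × 12)/13 = 1.48 at Week 17 for R = 13, and 1.50 after that.

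**The case against.** A reader might infer that every behaviour change in this analysis is understated. The windows do not support that. The Week 5 window contains no post-injection time, so a change starting at first injection is measured from a clean baseline and appears almost in full from Week 17. Where behaviour rises from enrolment, the injection-phase contrast is overstated. Week 9 exists only in Cohort 2, so in the pooled model it distorts the early shape of the trend and does not shrink everything.

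A reader might also infer that the weeks after the last injection (12 of 36 in Cohort 1, 8 of 36 in Cohort 2) are never observed, because section 9.10 groups Week 41 with the tail visits. That does not follow. The questionnaire is given at Week 41, section 7.1 runs the injection phase to Week 41 for those who complete the course, and section 4.4 lists Week 41 apart from the tail visits. Only the label needs settling.

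Other defences carry weight:

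- The trial is randomised and double-blind, and both arms of a cohort share the same windows. If the arms truly do not differ, the comparison is not biased. A real early difference is still diluted, and within-arm change is itself a planned test.
- Section 7.2 allows a Week 5 baseline in some cases, so the choice looks deliberate. It remains at odds with the endpoint in section 3.2, and with this recall it does not isolate the oral phase.
- The questionnaire is not shown, and in the outcome list the recall phrase could attach to the last item alone. The later sentence on the trend applies it to risk behaviour generally, and the SAP states no other recall.
- Robust standard errors deal with within-person correlation. They do not correct a window that covers the wrong period.

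**Conclusion.** The point holds in limited form. The Week 5 test shows only about 38-42% of a change that starts at enrolment. The Cohort 2 Week 9 answer shows about a third (31-33%) of a change that starts at first injection. The Week 5 baseline passes part of any oral-phase change into the apparent injection-phase change, which can overstate it or create it. Estimates from Week 17 onward of a change starting at injection are sound, and so is a null comparison between arms.

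This rests on two assumptions: that the stated recall applies at every visit, and that 3 months means 12 to 13 weeks. The fractions suit counts of acts. They are approximate for numbers of distinct partners, which do not add up over time. The endpoint is secondary and behavioural, so the change is advisable, and the primary safety and tolerability analyses are unaffected.

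**What to change.** In section 9.10:

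- Use the enrolment questionnaire as the baseline for the GEE, in line with section 3.2.
- Model Weeks 17, 29 and 41 in Cohort 1 and Weeks 17, 25, 33 and 41 in Cohort 2. State that Week 41 counts in the injection phase, as section 7.1 has it.
- Report Week 5 and Cohort 2 Week 9 descriptively, with the window overlap stated.
- Say in Table 24 and Figure 10 that baseline means enrolment.

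All these questionnaires are already scheduled, so the change is SAP wording only. The formal test of change in the oral phase alone is given up, but the recall window cannot support it. The model then estimates total change since enrolment and no longer tries to split it by phase. Consecutive Cohort 2 windows from Week 17 still overlap by 4/12 = 33% to 5/13 = 38%. This smooths the trend a little but brings in no pre-enrolment time.

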2.4 Schema

Cohort 1

W = Week

Cohort 2

The 110 participants in Cohort 1 and 90 participants in Cohort 2 were randomized to one of the two study arms with an active GSK 744 to placebo ratio of 3:1, stratified by gender and region (US and non US), as follows:

Cohort 1

Arm 1: 82 participants received daily oral 744 (30 mg tablets) for 4 weeks, followed by an one week washout period, to establish safety and tolerability, followed by intra-muscular (IM) gluteal injections of 800 mg of 744LA (administered as two sequential 400 mg gluteal injections) at three time points at 12 week intervals as: Week 5, Week 17, and Week 29.

Arm 2: 28 participants received daily oral matching placebo and IM injections of vehicle-matched placebo on the same schedule as Arm 1.

Cohort 2

Arm 1: Approximately 66 participants will receive daily oral 744 (30 mg tablets) for 4 weeks, followed by a one week washout period, to establish safety and tolerability, followed by intra-muscular (IM) gluteal injections of 600 mg of 744LA (administered as one 600 mg gluteal injection) at five time points at 4 and 8 week intervals as: Week 5, Week 9, Week 17, Week 25, and Week 33.

Arm 2: Approximately 22 participants will receive daily oral matching placebo and IM injections of vehicle-matched placebo on the same schedule as Arm 1.

All participants will receive HIV testing with pre- and post-test counseling, in addition to risk-reduction counseling and condoms and lubricant. All participants will be followed according to the Schedule of Evaluations and Procedures provided in HPTN077 protocol Appendices I-IV.

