4 STUDY DESIGN

4.1 Participants

200 men and women at low to minimal risk for acquiring HIV infection, ages 18 to 65, randomized 3:1, with approximately 150 in the active drug arm, and 50 in the placebo arm. It is anticipated that approximately 60% of the enrolled participants will be women.

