9.8 Study Medication Satisfaction Questionnaire

The Study Medication Satisfaction Questionnaire (SMSQ) will also be used to assess subject tolerability and satisfaction to the study medication in this trial. The SMSQ is a modified version of the current HIV Treatment Satisfaction Questionnaire (HIVTSQ) that does not include questions pertaining to treatment but rather study medication. The SMSQ is a 12-item self-reported scale that measures overall satisfaction with medication, general satisfaction/clinical, satisfaction with lifestyle/ease, and each individual satisfaction. This study uses the SMSQs (status version) and the SMSQc (change version).

The SMSQs will be administered at the following time points: Week 6, Week 18, and Week 30 in Cohort 1 and Weeks 6, 10, 18, 26, and 34 in Cohort 2. The SMSQc will be administered at Week 18 in Cohort 1 and Week 10 in Cohort 2.

For each question the responses will be summarized by the proportion of participants reporting the response on the Likert scale out of all those that answered the question at visit by the treatment arm. An overall treatment satisfaction score will be calculated for each participant at each visit. To evaluate the participants' experience of the medication with injection comparing to the experience of medication with tablets during the first 4 weeks of the study, the score derived from SMSQc will be summarized by treatment arm and compared between the treatment arms using t-test and using the linear regression model to adjust for site effect (US sites vs. Non-US sites). To evaluate the participants' experience of the medication with injection, the scores derived from SMSQs will be summarized by treatment arm and visit and compared between the treatment arms over time using GEE model to account for the correlations of the scores over time and will be evaluated the changes over time within the treatment arms. The analyses will be done by Cohort and in aggregate.

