9.9 Acceptability Questionnaire

Baseline acceptability questionnaire (BAQ) will be administered at baseline Week 0 visit in both cohorts. Follow-up acceptability questionnaire (FAQ) will be administered at Weeks 6, 18, and 30 in Cohort 1; at Weeks 6, 10, 18, 26, and 34 in Cohort 2.

The scores will be derived from the items in BAQ/FAQ at each visit and then will be compared between the treatment arms. The scores derived from BAQ will be summarized and compared between the treatment arms using t-test and using the linear regression model to adjust for site effect (US sites vs. Non-US sites). The scores derived from FAQ will be summarized and compared between the treatment arms using GEE model to account for the correlations of the scores over time and will be evaluated the changes over time within the treatment arms. The data will be analyzed by cohort and in aggregate.

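### The gender-stratified count models in SAP 9.10 rest on robust standard errors with only about 20 placebo men and 30 placebo women, so arm-by-time tests are too liberal and intervals too narrow

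*SAP*

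**What the plan says.** SAP 9.10 pools the cohorts and models several sexual risk counts, which "are as the outcomes and are assumed with a negative binomial distribution". It adds: "Both analyses will be stratified by gender and adjusted for other demographic variables such as age and race/ethnicity". For the injection-phase analysis, "a linear and quadratic time and time interactions with the treatment are included in the model". On inference it says only: "Robust standard errors will be used to account for within-person correlation".

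SAP 9.8 has the satisfaction (SMSQ) scores "compared between the treatment arms over time using GEE model to account for the correlations of the scores over time", and 9.9 has the follow-up acceptability (FAQ) scores "compared between the treatment arms using GEE model to account for the correlations of the scores over time". Both run by cohort and in aggregate. Neither names a standard-error type.

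On numbers, SAP 2.4 gives 28 placebo participants in Cohort 1 and, for Cohort 2, "Approximately 22 participants will receive daily oral matching placebo and IM injections". SAP 4.1 gives about 150 active and 50 placebo participants, and "It is anticipated that approximately 60% of the enrolled participants will be women".

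None of these sections mentions a small-sample correction, a t or F reference distribution, or a permutation check.

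**The concern.** The sandwich variance is built from squared residuals, summed over participants. Fitted residuals are smaller than true errors, so the estimate is biased downward when one arm has few participants. It is also noisy, and a normal or chi-square reference ignores that noise. Under 3:1 allocation the placebo arm contributes about three quarters of the variance of a difference, so the placebo count matters more than the total. Skewed counts make both problems worse, because a few participants with high counts dominate the estimate.

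At stake is whether a reported arm difference in the course of sexual risk behaviour, a listed secondary objective, can be taken at its nominal error rate. SAP 9.10 names several outcomes and fits each in two genders, so there are several chances of a false difference.

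**Working it through.** **1. Placebo numbers.** At 3:1, placebo = N/4: 110/4 = 27.5 (SAP 28), 90/4 = 22.5 (SAP about 22), 200/4 = 50 (SAP about 50). By gender: 0.60 × 50 = 30 women and 0.40 × 50 = 20 men. These are upper figures for the injection phase, since dropout lowers them.

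**2. Best case in closed form.** Take a simple difference of arm means with normal errors and equal variances.
- Bias of the plain sandwich: b = [(n0−1)/n0² + (n1−1)/n1²] / (1/n0 + 1/n1).
- Satterthwaite df: ν = (1/n0 + 1/n1)² / [1/(n0²(n0−1)) + 1/(n1²(n1−1))].
- Rejection with a normal reference: P(|t_ν| > 1.96√b).

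| Placebo v active | √b | ν | Rejection |
|---|---|---|---|
| 20 v 60 | 0.979 | 32.6 | 6.4% |
| 22 v 66 | 0.981 | 36.0 | 6.3% |
| 28 v 82 | 0.985 | 46.8 | 6.0% |
| 30 v 90 | 0.986 | 49.8 | 5.9% |
| 50 v 150 | 0.992 | 84.0 | 5.5% |

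Well-behaved data on 1 df therefore cost only about 1 point. Larger errors need skewed counts or multi-df tests.

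**3. Counts, as in 9.10.** Simulation without an arm effect: 2,500 replicates per scenario, Monte Carlo standard error about 0.4 to 0.9 points. The model had a log link, independence working correlation, arm, linear and quadratic time, both arm interactions, age and race. Assumptions, none given in the SAP: mean 0.3 to 8, between-person dispersion 0.3 to 4, within-person dispersion 0.2 to 1.5, no dropout, two-sided 5%.

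| Model | 1 df, plain | Joint 2 df, plain | Median SE / true SD (arm term) | 1 df, corrected | Joint 2 df, corrected |
|---|---|---|---|---|---|
| Men, 20 v 59 | 5.7–16.4% | 8.1–26.5% | 0.66–0.95 | 3.4–12.8% | 4.6–19.2% |
| Women, 30 v 89 | 5.5–12.8% | 8.0–19.6% | 0.74–0.94 | 4.2–10.3% | 5.1–14.9% |

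Here, corrected means Mancl-DeRouen with a t/F reference on (placebo n − 1) df. The low ends are a mean of 2 with little overdispersion. The top of each plain range comes from a mean of 0.3 with strong overdispersion. In that scenario 239 of 2,500 male fits failed (9.6%), so sparse counts are a modelling problem too. A separate simulation gave about 8–11% on 1 df and 7–19% on the joint test.

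**4. Scores, as in 9.8 and 9.9** (within-person correlation assumed 0.5, normal or skewed errors):
- By cohort, linear time: 5.1–6.8% on 1 df and 6.4–8.5% on 2 df. Corrected: 3.2–4.6% and 3.6–5.2%.
- By cohort, visit as a category, no dropout: Cohort 2 (64 v 21) 12–13% for the 5-df joint arm test, 10% for arm-by-visit and 6–6.5% for the average effect. Cohort 1 (80 v 27) 8%, 7% and 6%.
- With 3% dropout per visit, the Cohort 2 figures become 13–15%, 10–13% and 7–8%.
- Aggregate (50 v 148): 4.7–6.2% on 1 df and 6.3% on 2 df.

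**The case against.** Four objections deserve an answer.

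- **A reader might infer that the SAP prescribes uncorrected standard errors throughout.** It does not. Only 9.10 names robust standard errors, and no section adopts or excludes a correction. This stands for 9.8 and 9.9. In 9.10, the plain sandwich is the natural reading of robust standard errors with nothing added, so the plan leaves the liberal choice open.
- **A reader might infer that every GEE analysis has only 20 to 30 placebo participants and rejects up to 20% of the time.** The documents do not support that. The aggregate SMSQ and FAQ analyses have about 50 placebo participants and are near nominal. High rates for scores appear only with visit as a category and a multi-df test, which the SAP neither specifies nor rules out. The top of the count range needs sparse or strongly overdispersed data, and mostly the joint test. The wording of 9.10 on trends can equally be read as separate 1-df tests, for which the range is about 6–16%. Sparse counts are nevertheless plausible: SAP 4.1 enrols people at low to minimal risk, and 9.10 models unprotected acts with HIV-positive partners.
- **A reader might infer that a false signal would feed into phase III planning.** SAP 5.2 ties phase III to safety and pharmacokinetic summaries, and 5.3 ties decisions to the Week 41 safety and tolerability results. No decision rule uses a GEE p-value. The final-report lists include sexual risk (Table 24, Figure 10) but no SMSQ or FAQ table.
- **A corrected sandwich does not cure the worst cases.** This stands and shapes the fix.

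**Conclusion.** The point holds for the gender-stratified count models in 9.10. Read in the ordinary way, the plan gives tests that reject about 6–16% of the time on 1 df at a nominal 5%. For the joint interaction test the figure is about 7–20%, and up to about 26% for the sparsest male counts. Standard errors for the arm term run at about 0.66 to 0.95 of the true spread, so intervals are too narrow. The direction is firm. The size depends on assumed means, dispersions and choice of test, and the 5% level is inferred from the 95% intervals used elsewhere in the SAP.

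For the by-cohort SMSQ and FAQ models the effect is mild: about 5–8% for a simple arm contrast and 6–9% on 2 df. It reaches about 7–13% (up to 15% with dropout) only for multi-df tests with visit as a category. The primary safety and tolerability comparisons use Fisher's exact test and are untouched. The change should be made, but no primary conclusion depends on it.

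**What to change.** In 9.10:
- Take the arm and arm-by-time p-values from re-randomisation within the gender and region strata, separately by cohort, using the model's Wald statistic. This is the main repair, because it does not rely on the variance estimate being right. It tests the null of no arm effect on anyone at any visit, and the SAP should say so.
- Report intervals from a bias-corrected sandwich (for example Mancl-DeRouen) with a t/F reference based on the placebo count. Note that this correction alone does not restore 5% for overdispersed counts.
- State whether the linear and quadratic interactions are tested separately or jointly, and what is done when a sparse outcome fails to converge.

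In 9.8 and 9.9, for the by-cohort models, state either the same corrected sandwich with a t/F reference or a linear mixed model with Kenward-Roger degrees of freedom. Also say how visit is coded.

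The cost is a few sentences of SAP text, slightly wider intervals and a little more programming for the re-randomisation. Data collection does not change.

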4.7 Randomization

Enrolled participants are randomized to one of two study arms with an active GSK1265744 to placebo ratio of 3:1 in two cohorts. The arm randomization is stratified by

gender and region (US and non-US sites) and done in blocks to ensure balanced treatment assignments within each gender and region (US and non-US). The randomization scheme is generated, operationalized and maintained by HPTN SDMC using Frontier Science & Technology Research Foundation, Inc. (FSTRF) system. Additional details regarding the process of randomization are included in the SSP Manual.

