9.7.1 Association between Pharmacokinetics and Baseline Characteristics

To evaluate differential pharmacokinetics of 744LA in participants by age, gender, race, ethnicity, weight, body mass index (BMI), and smoking status, we will use GEE regression model to account the correlations of the PK parameters following three injections in Cohort 1 or five injections in Cohort 2. The analysis will be performed separately for each cohort. The associations between the PK parameters and the predictors will be tested in univariate models (include one predictor in each model) and

in a multivariate model (include all predictors). Each model will be adjusted for sites (US vs. Non-US sites) by cohort.

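### The pooled sexual-risk models in SAP 9.10 name neither region, a randomization stratum, nor cohort as covariates; adding both is a free improvement

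*SAP*

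**What the plan says.** SAP 9.10 describes two analyses of sexual risk behavior: change from enrollment to Week 5, and change from Week 5 during the injection phase. The outcomes are counts, taken as negative binomial, and the second analysis uses a GEE. On the model terms it says "The treatment and time are as covariates", and then "Both analyses will be stratified by gender and adjusted for other demographic variables such as age and race/ethnicity". On the time scale it says "In the second analysis, time is treated as a continuous variable measured in 3 months", with linear and quadratic terms and their interactions with treatment. On pooling it says "The data will be analyzed in aggregate".

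The behavioral questionnaire is given at enrollment and at injection visits: Weeks 5, 17 and 29 in Cohort 1, and Weeks 5, 9, 17, 25 and 33 in Cohort 2. Both cohorts then share tail visits from Week 41.

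SAP 4.7 sets out the design: "Enrolled participants are randomized to one of two study arms with an active GSK1265744 to placebo ratio of 3:1 in two cohorts". It names the strata as "gender and region (US and non-US sites) and done in blocks to ensure balanced treatment assignments within each gender and region (US and non-US".

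Elsewhere the SAP does adjust for region. For the PK GEE, 9.7.1 says "Each model will be adjusted for sites (US vs. Non-US sites) by cohort". The SMSQc regression in 9.8 and the BAQ regression in 9.9 also carry a US/non-US term.

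**The concern.** Randomization was stratified by two factors, gender and region. The models in 9.10 respect the first and do not name the second. They also pool two separately enrolled cohorts on different visit schedules without a cohort term. The list of adjustment variables is open-ended, but region and cohort are design factors rather than demographic variables, and a SAP should not leave a stratification factor to an illustrative list.

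Two things are at stake. First, the SAP tests a linear and a quadratic trend within each arm. When some visits are supplied by one cohort only, a constant difference between the cohorts can look like change over time. Second, if behavior differs between US and non-US sites, leaving region out keeps explainable variation in the residual.

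**Working it through.** The SAP gives no sample size, power or precision figure for this analysis, so there is no stated number to reproduce. The check has three parts.

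**1. Which models name region or cohort**

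| Analysis | Region named | Cohort handling |
|---|---|---|
| PK GEE (9.7.1) | yes | separate by cohort |
| SMSQc regression (9.8) | yes | by cohort and in aggregate |
| SMSQs GEE (9.8) | no | by cohort and in aggregate |
| BAQ regression (9.9) | yes | by cohort and in aggregate |
| FAQ GEE (9.9) | no | by cohort and in aggregate |
| Sexual risk models (9.10) | no | aggregate only |
| HIV incidence, exact Poisson (9.11) | no | not stated |
| Contraception subset, Fisher (9.12) | no | by cohort and in aggregate |

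No model has cohort as a covariate. The sexual-risk model is the regression that is run only on pooled data, so it is where a cohort term has the most to do.

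**2. How a cohort difference enters the trend**

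Arm sizes are from SAP 2.4: 82 active and 28 placebo in Cohort 1 (110), about 66 and 22 in Cohort 2 (88; the same section gives a cohort total of 90, which does not alter the result). Assume a flat mean of 2 events per 3 months in Cohort 1 and 3 in Cohort 2, a 1.5-fold difference, with no treatment effect. The pooled means by visit are then:

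- Weeks 5 and 17 (both cohorts): (110 × 2 + 88 × 3) / 198 = 484 / 198 = 2.44
- Weeks 9, 25 and 33 (Cohort 2 only): 3.00
- Week 29 (Cohort 1 only): 2.00

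Nothing changes within any person, yet the visit means move. The first analysis is not affected in this way, because both cohorts contribute at enrollment and at Week 5.

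**3. What the fitted model makes of it**

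The model in 9.10, ignoring demographics and the gender split, is

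log μ = b0 + b1·t + b2·t² + b3·A + b4·A·t + b5·A·t²,

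with A = 1 for active and t = (week − 5)/13. The large-sample GEE solution was found with variance μ + 0.5μ² and exchangeable working correlation ρ. The mean, the dispersion of 0.5, the cohort rate ratio and ρ are all assumptions; 9.10 does not state the working correlation. It lists Week 41 as a tail visit, while 7.1 ends the injection phase at Week 41, so both readings were run. The entries are fitted rate ratios against Week 5, where the truth is 1.000.

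| Cohort rate ratio | Week 33, injection visits only: ρ = 0 / 0.3 / 0.6 | Week 41, with Week 41 included: ρ = 0 / 0.3 / 0.6 |
|---|---|---|
| 1.25 | 1.015 / 1.006 / 1.002 | 0.984 / 0.995 / 0.998 |
| 1.5 | 1.027 / 1.010 / 1.004 | 0.972 / 0.991 / 0.997 |
| 2.0 | 1.043 / 1.016 / 1.006 | 0.954 / 0.985 / 0.994 |

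Hand check for 1.5-fold and ρ = 0: b1 = −0.0323, b2 = 0.0207, t = 28/13 = 2.154. Then exp(−0.0323 × 2.154 + 0.0207 × 4.639) = exp(0.0265) = 1.027.

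For the arm comparison, the active share is 82/110 = 74.5% in Cohort 1 and 66/88 = 75.0% in Cohort 2. At Week 5 in the 1.5-fold case the active mean is (82 × 2 + 66 × 3)/148 = 2.446 and the placebo mean is (28 × 2 + 22 × 3)/50 = 2.440, a ratio of 1.002. The treatment-by-time coefficients are at most about 0.0005 in absolute value on the log scale across all settings. With a cohort main effect in the model, the false time terms are zero by construction in this scenario.

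**The case against.** The strongest reply is that the omission does almost no harm. Pooling is deliberate: SAP 3.2 defines this endpoint in aggregate only. Region was balanced between arms by blocked randomization, and 9.10 specifies robust standard errors, so leaving region out costs at most some efficiency and does not invalidate the test. The trend leak nearly vanishes once a realistic within-person correlation is used. The covariate list is open and does not exclude region. All of this stands, and it limits the point to a refinement of a secondary analysis.

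Two stronger readings are tempting and should be resisted. A reader might infer that 9.10 is the odd one out and that the other secondary models all adjust for region and cohort. The table above shows otherwise: the SMSQs and FAQ GEEs, which are the closest analogues, name no region term, the exact tests are unadjusted, and no model has a cohort covariate.

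A reader might also expect a sizeable gain in precision, by taking the share of between-person variance that region and cohort explain and applying the linear-model factor √(1 − R²). That does not carry over. The questions in 9.10 concern change over time and its difference between arms, where differences in level between people largely cancel, and count variation within a person remains whatever is adjusted for. The SAP gives no variance data from which to size the gain.

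The objection does not answer the within-arm trend tests. The leak there is small but avoidable, and its size and sign depend on choices that 9.10 leaves open.

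**Conclusion.** The point holds as a free improvement. The models in 9.10 pool the cohorts and name neither region nor cohort. For an assumed 1.5-fold cohort difference, the within-arm trend is distorted by about 3% at Week 33 under independence and by under 1% at a correlation of 0.6. Over the full range assumed here (1.25-fold to 2-fold) the distortion is at most about 4% to 5% at the last modelled visit, upward or downward depending on whether Week 41 is included. These figures rest on flat true means, complete visits and no gender split; the actual cohort difference is not in the document. The comparison of trends between arms is essentially unbiased. The precision gain is likely modest and is not quantified.

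**What to change.** Keep the aggregate analysis. In 9.10, add one sentence stating that both behavior models include region (US vs. non-US) and cohort as fixed main effects, in addition to the gender stratification and the demographic adjustment already planned. With cohort in the model, a constant difference between cohorts no longer feeds the time terms, whatever working correlation is used.

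The cost is SAP wording and two degrees of freedom per model. No data collection, visit or sample size changes. A cohort-by-treatment test is not needed: with about 22 to 28 placebo participants per cohort, split further by gender, it would tell the reader little.
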